Study Title

Improving TraNsplant Medication Safety through a Technology and Pharmacist Intervention (ISTEP)

Objectives

Primary

1. 24-month rate of hospitalization and emergency room visits compared between the intervention and usual care groups

Secondary

2. 24-month total estimated health care costs, compared between the intervention and usual care groups
3. Estimated graft survival rates, compared between the intervention and usual care groups and defined as the proportion of patients that continue to have a functioning allograft at the end of the 24-month study
4. Estimated patient survival rates, compared between the intervention and usual care groups and defined as the proportion of patients alive at the end of the 24-month study
5. Potential medication safety issues, defined as the proportion of patients with the following, based on automated reports for the transplant medication dashboard:
 - a. Percent of patients with missing labs
 - b. Percent of patients alarming lab values without follow up scheduled
 - c. Immunosuppression adherence, estimated using the proportion of days covered (PDC)
 - d. Percent of patients on significant drug interaction without a immunosuppressant level
 - e. Percent of patients with hospital discharge or ED visit without follow up scheduled
6. Proportion of alerts that were deemed clinical relevant and actionable by the intervention pharmacists
7. Proportion of interventions that were deemed to be accepted when made to other providers based on dashboard reporting information
8. Average time required to respond to each alert

Design and Outcomes

This is a 24-month, prospective, multicenter, cluster-randomized, parallel-arm, controlled clinical trial assessing the impact of a pharmacist-led technology-enabled intervention designed to improve immunosuppression medication safety

in veteran organ transplant recipients. The study includes 10 sites, five sites randomized to standard clinical care and five to standard care plus the technology-enabled pharmacist intervention.

Study efficacy will be determined by comparing the rates of hospitalizations and ER visits between intervention and control study site veteran organ transplant recipients, while adjusting for baseline patient, provider and facility characteristics. Secondary measures include comparing estimated healthcare costs and determining dashboard functionality, dashboard actionability and pharmacist intervention types and acceptance rates. We will also assess the overall incidence and severity of drug-related problems and graft and patient survival rates and compare these between the intervention and control sites.

Interventions and Duration

The study will randomize 10 sites to usual care or usual care plus intervention in a parallel arm design and study duration will be 24-months.

The intervention will include a pharmacist that utilized a dashboard system to identify veteran organ transplant recipients with the potential of immunosuppressant medication-safety issues. The technology component of this intervention consists of the use of a dashboard system that performs population-level surveillance of organ transplant recipients and identifies those with potential drug-related problems, including non-adherence to immunosuppression medications, drug interactions, missing and worrisome trends in labs and recent hospitalizations and ED visits; then providing a real-time alert to the pharmacist, who will determine its relevance and intervene in an appropriate protocol-guided manner.

Sample Size and Population

There will be 10 sites included in this study with an estimated average of 169 veterans per site, totaling 1,689 veterans across the entire study population, divided approximately equally between the intervention and usual care groups

The patient population will consist of veterans that received solid organ transplants (kidney, liver, pancreas, heart, or lung) and receive their immunosuppression medications through the VA system. Patients will be identified using ICD-9 or 10 codes and VA medication prescription information.

1 STUDY OBJECTIVES

1.1 Primary Objective

Hypothesis:

1. Veterans in the intervention group will have significantly lower rates of hospitalizations and emergency room visits, as compared to the control group, by the end of the 24-month study

Objective:

1. Through a 24-month prospective, parallel arm, cluster-randomized, controlled multicenter study, measure the effectiveness of a pharmacist-led, technology-enabled intervention on reducing the rate of hospitalizations and emergency room visits in Veteran organ transplant recipients, as compared to usual care

1.2 Secondary Objectives

Hypotheses:

1. Veterans in the intervention group will have significantly reduced health care costs, as compared to the control group, by the end of the 24-month study
2. The immunosuppressant dashboard system will provide near real-time, actionable alerts that will allow the pharmacist to conduct timely interventions on potential or ongoing drug-related problems

Objectives:

1. 24-month estimated health care costs, compared between the intervention and usual care groups
2. Estimated graft survival rates, compared between the intervention and usual care groups
3. Estimated patient survival rates, compared between the intervention and usual care groups
4. Potential medication safety issues, defined as the proportion of patients with the following, based on automated reports for the transplant medication dashboard:
 - a. Percent of patients with missing labs
 - b. Percent of patients alarming lab values without follow up scheduled
 - c. Immunosuppression adherence, estimated using the proportion of days covered (PDC)

- d. Percent of patients on significant drug interaction without a immunosuppressant level
- e. Percent of patients with hospital discharge or ED visit without follow up scheduled
- 5. Proportion of alerts that were deemed clinically relevant and actionable by the intervention pharmacists
- 6. Proportion of interventions that were deemed to be accepted when made to other providers based on dashboard reporting information
- 7. Average time required to respond to each alert

2 BACKGROUND AND RATIONALE

2.1 Background on Condition, Disease, or Other Primary Study Focus

Within organ transplant, despite dramatic improvements in acute rejection rates, long-term graft survival has not improved to nearly the same degree. In kidney transplant, since 2003, there has been a 50% reduction in acute rejection rates; yet, during this same period of time, the allograft half-life has only increased by a modest 0.6 years.^{6,7} The most recent report from the Scientific Registry of Transplant Recipients (SRTR) demonstrates a historically low one-year acute rejection rate of 10%, with a suboptimal five-year graft survival rate of 70%.⁴ Drug-related problems, which encompass medication errors, non-adherence and adverse drug events, are a predominant cause of deleterious clinical outcomes in kidney transplant recipients; most notably, graft loss.²² Our previous research, as well as studies from other groups, has demonstrated that approximately two-thirds of transplant recipients will experience at least one medication error.¹¹⁻¹³ Of more concern, nearly one in eight kidney transplant recipients experience a medication error which directly contributes to hospitalization and doubles the risk of graft loss. These medication errors are usually the result of unintentional non-adherence: patients have difficulty obtaining medications, gets confused from the fragmented care they receive or forget to take medications in a timely manner.¹⁴ Non-adherence has now been recognized as a major contributor to late acute antibody mediated rejection (AMR), the development of donor specific antibodies (DSA) and subsequent graft loss. In a landmark study by Sellares et al, 315 kidney transplant recipients were followed for roughly three years post-transplant; 47% of the 50 allografts that failed during this time were due to AMR; 32% of patients were identified as non-adherent and one-half of all AMRs were due to this. Remarkably, medication non-adherence was 10 times more frequent in patients with graft failure (32% vs. 3%, $p<0.001$).²² As most medication non-adherence is unintentional, with the proper monitoring and follow-up, this devastating risk factor is modifiable. Other drug-related problems, beyond non-adherence, also significantly contribute to deleterious post-transplant events. A study by Friedman et al demonstrated that of 149 medication errors identified in 93 ambulatory organ transplant recipients, 44% were due to iatrogenic causes, including 13% from a prescribing error and 13% from a dispensing error. Importantly, 26% of these errors led to clinical significant events, including

laboratory abnormalities (8%), physical issues (5%), hospital admission (8%) and an outpatient intervention (8%). Thus, to improve medication safety, interventions should not only focus on the patient, but also engage the health care providers.¹¹

Although immunosuppression is effective at preventing rejection, adverse drug events are nearly universal and associated with significant morbidity. Several studies suggest that adverse drug events, particularly infection from over-immunosuppression and calcineurin inhibitor nephrotoxicity, may be a predominant cause for the discordance between reductions in acute rejection and lack of improvements in graft survival.

Parasuraman et al demonstrated that infectious etiologies have surpassed rejections as the leading cause of graft loss.⁹ Our previous research demonstrates that immunosuppressant adverse drug events are associated with medication errors; patients that experience medication errors leading to hospitalization have 2.3 times the risk of developing at least three adverse drug events ($p=0.020$).¹⁴ In other comorbidities, adverse drug events have clearly been established as a major risk factor for medication non-adherence.²³⁻²⁶ Therefore, early recognition of adverse drug events in transplant recipients will likely help prevent downstream clinical sequelae, including non-adherence and irreversible immunosuppressant toxicities. Research demonstrates that clinical pharmacists have the unique education and training to both identify these events early, while also developing strategies to mitigate or resolve the associated sequelae.^{16,17,27-31}

Also of concern with the use of chronic immunosuppression therapy in the ambulatory care setting are drug interactions. The calcineurin inhibitors and mTOR inhibitors, which are widely utilized immunosuppressants, are metabolized through the cytochrome P450 3A4/5 enzyme system, making them prone to interactions. Due to their effects on the renal and nervous system, these drugs are also frequently associated with pharmacodynamic drug interactions and drug-disease interactions. This includes interactions with classes of medications that are the most frequently prescribed in the outpatient setting, such as NSAIDs and ACE inhibitors. These interactions can result in an acute and dramatic reduction in renal function and electrolyte disturbances, particularly hyperkalemia.^{32,33} The impact of drug-related problems leading to graft loss on clinical and economic outcomes cannot be overstated. Annual death rates are more than three times higher in those with kidney allograft failure (9.4%), as compared to those with a functioning transplant (2.8%).³⁴ A well-functioning kidney transplant has also been shown to dramatically reduce the progression of cardiovascular disease and associated events.³⁵⁻³⁷ In other organ types, graft loss universally leads to either retransplant or death. In terms of cost, transplantation is highly cost-effective. However, due to high and varied peri-operative costs associated with this surgery, the break-even point can range from two to 11 years after transplant.^{38,39} Once a kidney transplant fails, patients return to dialysis and costs to provide care accrue at a significantly higher rate.^{40,41} Our research indicates that kidney transplant recipients that experience clinically significant medication errors spend five more days in the hospital for readmissions, costing more than \$18,000 per case.¹⁴ These data, taken in its entirety, establishes the need for innovative interventions designed to improve medication safety and reduce drug-related problems in transplant recipients, by decreasing medication errors, non-adherence and adverse drug events;¹⁰ Such medication safety improvements are needed to demonstrate significant progression in

the optimization of long-term graft outcomes and patient survival.

2.2 Study Rationale

Previous research provides evidence that this clinical trial is grounded on a strong conceptual model explaining the etiologies of medication safety events in transplant patients and supported by empirical evidence demonstrating the use of technology and pharmacist-led interventions can improve outcomes in transplant patients. The specific rationale for this study are based on the following:

Medication Safety Issues in Transplantation:

- Medication safety events are common in transplant recipients. In an analysis we conducted of 200 prospectively monitored transplant recipients, significant medication errors occurred in 64% of patients, with immunosuppressants associated with the error 48% of the time. Patient-related issues (taking the wrong dose prescribed or missing doses) caused 68% of these errors, with provider and systems issues accounting for the remaining third. Significant adverse drug events, defined as the Common Terminology Criteria for Adverse Events (CTCAE) grade 3 or higher, occurred a total of 327 times and within 87% of the study cohort. Patients that experienced a significant medication error contributing to a hospitalization developed more adverse drug events (2.1 ± 1.0 vs. 1.6 ± 1.1 , $p=0.030$).¹⁴
- Previous research has demonstrated that transplant recipients numerous risk factors for the development of medication safety events, including: taking >10 medications concomitantly with more than 30 doses ingested per day, being prescribed narrow therapeutic index medications that are prone to drug interactions, taking chronic immunosuppressants with known debilitating side effects and having frequent dosage adjustments that occur during distantly, over the phone, during chart reviews. Additionally, long-term ambulatory transplant recipients usually receive care across multiple health care organizations; thus fragmented care, omissions, duplications and discrepancies in medication regimens are common within these patients. We have also established this as a major issue facing Veteran transplant recipients.^{3,10-13}

Pharmacist-Led Interventions to Improve Medication Safety in Transplantation:

- Previous studies demonstrate that interdisciplinary quality improvement endeavors, which include the empowerment of pharmacists to implement initiatives aimed at improving medication use, can substantially improve medication safety in transplant recipients during the perioperative phase. This data demonstrated a 40% reduction in adverse drug events leading to hospitalization, 14% reduction in length of stay >3 days and 50% reduction in 14-day readmissions. Our follow-up study, which measured the impact of a pharmacist-led formal medication reconciliation initiative, demonstrated that, on average, 2.3 medication errors per

transplant recipient discharge were prevented (3.4 vs. 1.1, $p<0.001$, respectively); although, medication errors were still apparent in a significant number of discharges, establishing the need of pharmacist involvement in the ambulatory phase of care for these high-risk patients.^{16,17}

Medication Safety in Veteran Transplants:

- Veteran transplant recipients are embedded within highly complex inter-facility systems of care, such that medication safety monitoring and care coordination in the ambulatory care setting is often fragmented and suboptimal. Our previous research has demonstrated that nearly two-thirds of Veteran transplant recipients are dual-users; with 62% having multiple providers managing the same conditions. This leads to a significant number of duplications and omissions in care. Medication discrepancies between systems are nearly universal as well. Thus, provider and system-level issues represent substantial reinforcing and enabling factors driving medication safety events in Veteran transplant recipients.³
- We completed an interrupted time series analysis, demonstrating significantly improved adherence to appropriate immunosuppression laboratory monitoring by using a population surveillance dashboard to identify Veteran transplant recipients with missing laboratory data, allowing the pharmacist to efficiently intervene by engaging the Veterans to either schedule labs or document non-VA care. Using segmented regression, we demonstrated a 38% improvement in monitoring ($p<0.001$), at a rate of 4.7% improvement per month for the first six months of the intervention ($p<0.001$).¹⁸ Thus, we have strong preliminary data that the dashboard is functional and can be an effective instrument to identify Veterans needing attention in a time-sensitive and efficient manner. This dashboard system is currently being utilized at multiple sites (one in VISN 7 and several in VISN 12). For this proposal, we plan to expand the dashboards functionality and incorporate its use by pharmacists as part of clinical care at the 5 sites randomized to the intervention arm of this study.

The cluster-randomized design of this study was chosen for a number of important reasons. First, this study design will allow investigators to test a promising intervention against a similar control group with respect to patient constitution and time. The use of randomization at the site level will allow us to complete the 24-month study within a reasonable period and within the budget constraints. Using the cluster randomized parallel design at 10 sites will provide sufficient patient numbers to meet statistical power to detect clinically meaningful differences in health care utilization.

Randomization at the patient-level, as opposed to the site, would not be feasible, as there would be a high probability of cross-contamination based on the intervention proposed and the technology component, which uses site-specific population surveillance. Additionally, randomization at the patient-level would substantially prolong enrollment, thus making completion within 4 years infeasible. Other trial designs were considered and discussed with the investigational group, including stepped-wedge, interrupted time series, one group pre-post test, one group post-test only and a

traditional patient-level randomization. The stepped wedge is the best alternative to our proposed study but would provide limited time to evaluate outcomes at some of the sites. Given the proposed intervention type, the use of population-surveillance technology, the number of sites recruited and the time and budget constraints, the investigative team felt that the parallel-group, cluster randomized controlled trial was the strongest in terms of methodology, internal validity, statistical power, feasibility and likelihood of success.

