addressed. These include ensuring the patient is taking the correct dose, ensuring the level is a true trough value, checking for new drug interactions and adjusting the dose when necessary. When medication non-adherence is identified as a potential issue, the pharmacist will determine if it is deliberate or unintentional. Strategies to address deliberate non-adherence include removing perceived or actual barriers, using motivational interviewing, and addressing side effects and cost issues. For unintentional non-adherence, pharmacists can implement trigger reminder strategies, simplify regimens, and re-educate. Within drug-interaction alerts, the intervention will focus on reducing the impact of these through changing of regimens (when appropriate), educating patients and/or providers and increased monitoring and surveillance.⁵¹ Alerts for medication coordination issues will encompass discharges from the ER and hospital and missed laboratory assessments. The intervention pharmacist will ensure accurate and safe medication regimens through medication reconciliation and improved medication safety surveillance through the scheduling and follow up of laboratory assessments.¹⁷

To ensure fidelity across sites and efficiency for providers, the specific day-to-day tasks involved with this intervention, which include assessing and intervening on the alerts and appropriate follow up with patient and providers, are fully developed and incorporated within the SOP manual. This manual was vetted by transplant clinicians, provided to each intervention site pharmacist, with appropriate training.

| Monitoring Variable | Absolute Value Thresholds | Trajectory Threshold |
|---|---------------------------|---|
| Laboratory Assessments – ONLY OUTPATIENT | | |
| Potassium (K) | <3 or >5.5 mEq/L | >30% Change |
| Bicarbonate (CO2) | <18 or >30 mEq/L | >30% Change |
| Blood Urea Nitrogen (BUN) | >40 mg/dL | >30% Increase |
| Creatinine (Cr) | >2.5 mg/dL | >20% Change |
| Glucose (Gluc) | <60 or >300 mg/dL | >30% Change |
| Calcium (Ca) | <7 or >10 mg/dL | >30% Change |
| Magnesium (Mg) | <1.0 or >2.5 mEq/L | >30% Change |
| Phosphorus (PO4) | <2.0 or >5.0 mg/dL | >30% Change |
| White Blood Cell (WBC) Count | <3.0 or >15.0 cells/mm3 | >30% Change |
| Hemoglobin (Hgb) | <8 or >15 gm/dL | >20% Change |
| Platelets (Plt) | <50 or >500 cells/mm3 | >30% Change |
| Alanine Aminotransferase (ALT) | >160 U/L | >30% Increase |
| Total Bilirubin (T Bili) | >1.5 mg/dL | >20% Increase |

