process measures will serve to both assess the dashboard functionality and allow for modification to improve the efficiency of the intervention. The time assessment data will allow us to determine the amount of time and effort implementing this system requires, as it relates to embedding it into normal workflow processes. This information will be important if the dashboard is deemed effective and is disseminated for use to across the VA, as it will allow administrators to accurately assess the required pharmacist time needed for implementation. Finally, we will assess the type and magnitude of the interventions made using this dashboard to ensure study fidelity. The categorization and magnitude of these interventions will be assessed using the Overhage criteria, which is a well-established and validated method used in numerous studies, included several published by the investigators proposing this study.⁵² We will also assess the number of potential immunosuppression safety issues that occur and compare these between the two study arms. To do so, we will use the dashboard to provide monthly measurements of the following: percent of patients with missing laboratory assessments, percent of patients with alarming laboratory values without follow up scheduled, mean adherence to immunosuppression, based on refill timeliness and estimated using the PDC, percent of patients with a significant drug interaction without a immunosuppressant level and percent of patients with hospital discharge or ED visit without follow up scheduled. These will be measured in all patients and compared between the intervention and control groups at monthly intervals.

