10 DATA COLLECTION AND QUALITY ASSURANCE

10.1 Data Collection and Management

There will two general types of data used for this proposal, which includes operational data used for the dashboard system and research data to assess the impact of the intervention on outcomes. Operational data for the dashboard will be captured through querying the national VA CDW operational database using the FRS environment and stored in VISN 7 space already approved and allocated for this project. These data elements include diagnoses, laboratory values, medication regimens, refill histories, provider types and health care encounters (hospitalizations, ER visits), gathered and queried on a daily basis. The pharmacists at intervention sites will access their site-specific dashboard information stored on the server through an end-user permission access link that will restrict which patients are visible to ensure appropriateness of access to the correct PHI.

For the research component of the proposal, data will be captured through the research CDW and housed within the VINCI environment. We will link the VA data to the SRTR registry and CMS claims data. The CDW will provide data to assess outcomes including hospitalizations, ER visits and costs, as well as mortality. CDW data will also be used to assess interventions by querying pharmacists' progress notes. The CMS data will provide non-VA health care utilization, including hospitalizations and ER visits, as well as non-VA cost estimates. The SRTR data will provide all baseline donor, recipient and transplant characteristics as well as clinical outcomes, including acute allograft rejection, graft loss and death. We will also capture pharmacist entered data, which will be their assessments of the dashboard system. We will deploy a web-based data entry system that the intervention pharmacists will use during the first year of the intervention to assess the dashboard functionality. Queries answered by intervention pharmacists will include the number of alerts received, how many were considered clinically relevant/actionable, time to conduct the intervention and general intervention types. This data will be captured through the use of the REDCap system.

After data is cleaned and completely ready for analysis, we will remove identifiers from the final datasets. This will minimize the risk of loss of confidentiality. All data will be stored on the VINCI system and only approved study personnel will have access to this data.

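### The between-arm missing-labs outcome is read from the dashboard that only intervention pharmacists act on, so better recording of non-VA labs could pass for better monitoring

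*Combined protocol and SAP*

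**What the plan says.** - **Outcome.** The synopsis and Section 1.2 list the percentage of patients with missing labs among the medication-safety outcomes and take it from automated dashboard reports. Section 9.3.2 says "we will use the dashboard to provide monthly measurements of the following: percent of patients with missing laboratory assessments" and compares the result between arms every month in all patients.
- **Data source.** Section 10.1 says the dashboard queries VA operational data daily, and that pharmacists at intervention sites have access to their own site's view.
- **Handling of a missing-lab flag.** Section 2.2 describes the earlier interrupted time series with this dashboard as "allowing the pharmacist to efficiently intervene by engaging the Veterans to either schedule labs or document non-VA care". It then says the trial will expand the dashboard for use at the five intervention sites. For the trial itself, Section 5.1 speaks of "improved medication safety surveillance through the scheduling and follow up of laboratory assessments". Section 5.2 lists alert suppression as a training topic.
- **Care outside the VA.** Section 2.2 states that "nearly two-thirds of Veteran transplant recipients are dual-users".
- **Control sites.** Section 5.3 says pharmacists there do no routine daily surveillance of all transplant patients. At most sites, nurse coordinators or mid-level practitioners oversee labs.
- **External data.** Section 10.1 says "The CMS data will provide non-VA health care utilization" and names hospitalizations, ER visits and costs. Laboratory tests are not named.

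**The concern.** The dashboard is both the working tool of the intervention and the instrument that scores this outcome. A patient whose blood was drawn outside the VA looks untested in VA data. An intervention pharmacist is prompted to look into that patient and may establish that the lab was done elsewhere. At a control site nobody receives that prompt, so the same fact is less likely to reach the VA record.

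If an entry about outside care, or a suppressed alert, takes the patient out of the missing count, the arms differ in how completely outside labs are recorded as well as in how many labs are done. The plan has no rule that separates the two. At stake is the reading of a between-arm safety measure: Section 14 plans a manuscript on the intervention's impact on process measures, and a plan for implementing the dashboard across the VA.

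**Working it through.** The documents give no baseline rate, effect size or power for missing labs, so there is no stated figure to reproduce. The check has two parts.

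**1. Does the text allow the mechanism?**

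- *Is the scoring tool the one acted on?* Yes (synopsis, 1.2, 9.3.2, 10.1).
- *Is the prompt one-sided?* Yes. Daily alerts go to intervention pharmacists (3, 5.1).
- *Are there enough patients with outside care?* Nearly two-thirds are dual users (2.2). The share who have labs drawn only outside the VA is not given.
- *Is recording outside care one of the ways a flag is handled?* It was in the earlier work (2.2). The trial's intervention text names only scheduling and follow-up (3, 5.1). Carry-over is an inference from use of the same dashboard.
- *Does such an entry, or a suppressed alert, change the count?* Not stated anywhere.
- *Is the outcome derived from a source that alert handling cannot change?* Not stated in 9.3.2 or 10.1.

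If notes and suppressed alerts do not enter the count, this bias is absent. If they do, it is present. The plan leaves both open.

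**2. How large could it be?** All inputs here are assumptions.

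Let B be the share of patients flagged when nothing is documented, s the share of flagged patients who had the lab done outside the VA, and Δd the between-arm difference in the share of those documented. With no change in tests done:

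- apparent relative reduction = s × Δd
- apparent absolute difference = B × s × Δd

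Results for s = 25-50% and Δd = 50-100 percentage points:

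- smallest: 0.25 × 0.50 = 12.5%
- largest: 0.50 × 1.00 = 50%
- with B = 20%: the intervention arm shows 17.5% (20 × 0.875) down to 10% (20 × 0.50)
- with B = 30%: it shows 26.25% (30 × 0.875) down to 15% (30 × 0.50)
- absolute difference: 2.5 points (20% × 0.125) to 15 points (30% × 0.50)

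To see whether such an artefact could reach p<0.05 alone, take 5 v 5 sites of 169 patients, a single comparison of proportions, design effect 1 + 168 × ICC, and a noncentral t with 8 degrees of freedom, two-sided 0.05. The ICC of 0.05 comes from Section 9.2, where it is stated for the primary outcome (design effect 9.4). An ICC of 0.01 is an assumed lower value (design effect 2.68). Documentation at control sites is set to zero here, so Δd is the share documented in the intervention arm.

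| Control v intervention, recorded missing | s | Δd | P(p<0.05), ICC 0.05 | P(p<0.05), ICC 0.01 |
|---|---|---|---|---|
| 20% v 15% | 1/2 | 50% | 0.12 | 0.31 |
| 20% v 11% | 1/2 | 90% | 0.32 | 0.79 |
| 30% v 25% | 1/3 | 50% | 0.10 | 0.24 |
| 30% v 21% | 1/3 | 90% | 0.23 | 0.63 |

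The result depends heavily on assumptions that the documents cannot narrow.

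**The case against.** The strongest reply is that this concerns a data rule nobody outside the trial can see. The sentence about documenting non-VA care describes completed earlier work; the trial text names scheduling and follow-up; and the operational detail is in the SOP manual (Appendix I), which is not in the text available here. That is correct, so the point is conditional. It still stands, because the outcome definition in 9.3.2 should not depend on an alert-handling rule that it does not state.

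Control sites are also not idle. Section 5.3 gives nurse coordinators or mid-level practitioners responsibility for labs, Section 11.2 says the prompted care may also be given in the control group, and Section 2.2 says the dashboard is already in use at some VA sites. A reader might infer that no control site ever records outside labs, or that a control patient stays flagged for the whole 24 months. The documents support neither, only less frequent and unprompted recording. A difference in frequency is enough for bias, which is why the formula uses Δd and does not assume full against no documentation.

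Finally, finding an outside lab and making it known to the VA team is arguably care coordination, one of the intervention's targets. That has force, and it is a reason to report documented non-VA care as a category of its own. It is not a reason to count it as a lab newly done.

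**Conclusion.** The concern holds for the missing-labs comparison, conditionally. The outcome is scored by a tool that only one arm's pharmacists act on, most patients also have care outside the VA, and no rule protects the count from one-sided alert handling. If documentation or suppression clears the flag, the apparent relative reduction with no extra test is 12.5-50% under the assumed inputs. If it does not, this bias is zero.

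Three stronger readings are tempting and are not supported:

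- *That the earlier result was partly documentation.* Section 2.2 reports "we demonstrated a 38% improvement in monitoring" but does not say whether documented non-VA labs were credited in it.
- *That the adherence outcome is distorted in the same way.* That outcome is "mean adherence to immunosuppression, based on refill timeliness and estimated using the PDC". Recording an outside lab adds no refill days, every patient has at least one anti-rejection drug dispensed by the VA (4.1), and no section describes a route from documented outside care to the PDC.
- *That the main result is at risk.* The primary outcome is all-cause ER visits and hospitalizations from VA plus CMS data (9.3.1), which this mechanism does not touch.

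**What to change.** In Section 9.3.2, for the between-arm comparison:

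1. Derive missing labs by one rule in both arms, from raw VA laboratory results plus linked CMS claims. A pharmacist's note of non-VA care or a suppressed alert does not count as a lab done.
2. Show documented non-VA care as a separate category beside lab done and missing.
3. Keep the dashboard's own values as an operational process measure.

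The cost is mainly programming on a linkage already planned for non-VA encounters and for inpatient, outpatient and pharmacy costs (9.3.1, 9.3.2, 9.4). There are three limits. The result is available only after linkage, which follows study completion. It depends on the CMS files obtained including outpatient laboratory claims, which the plan does not state. Patients without Medicare claims would still rely on VA data, though equally in both arms.
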